8.1. Subject Inclusion Criteria for ADULT Subjects

Inclusion Criteria Specific for ADULT Subjects:

At Visit 1 (Screening), the subjects must meet all of the following inclusion criteria:

1. Provide signed written informed consent on the Institutional Review Board (IRB)/Ethics Committee (EC) approved Informed Consent Form (ICF).
2. Be 18 years of age or older on the date of signing the ICF and be able and willing to comply with all treatment and follow-up study procedures.
3. If a subject is a female of childbearing potential (i.e., not post-menopausal [within 12 months since the last menses] or not surgically sterile [less than 6 months from date of surgery]), she must have a negative urine pregnancy test and must use at least one of the following acceptable contraceptive methods during the study (as well as for 4 weeks following last dose in study).
 - Abstinence
 - Hormonal contraceptive method (including oral or transdermal contraceptives, injectable progesterone, progestin subdermal implants, progesterone-releasing intrauterine devices [IUDs]) initiated at least 28 days prior
 - Placement of a copper-containing IUD
 - Condom with spermicidal foam/gel/film/cream/suppository
 - Vasectomized male partner (surgery at least 6 months prior)

Male subjects capable of fathering children should use/ practice an acceptable contraceptive method, such as abstinence, condom or vasectomy (surgery at least 6 months prior) or other contraceptive method deemed adequate by the investigator throughout the course of the study (as well as for 12 weeks following last dose in study).

4. Must have a diagnosis of OAG (including Pigmentary Glaucoma or Pseudoexfoliative Glaucoma) or OHT in both eyes, or one eye with OAG and the other with OHT.
5. BCVA of +0.60 logMAR (Snellen equivalent 20/80) or better in each eye.
6. Central corneal thickness $\geq 480 \mu\text{m}$ and $\leq 600 \mu\text{m}$ in each eye.
7. Anterior chamber angle grade ≥ 2 (Shaffer scale) in each eye.

In addition to continuing to meet inclusion criterion 5 (BCVA), the subject must meet the following criteria at Visit 2 (Baseline, Day 1):

8. Completed the required wait/washout period.

9. At all time points of IOP measurements (08:00, 10:00 and 16:00) at Visit 2 (Baseline, Day 1), have IOP of ≥ 22 mmHg in at least one eye (the same eye), and ≤ 34 mmHg in both eyes.

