### **3.3. Sample Size Planning**

The sample size calculation was based on a two-sided Type I error rate of 5% and a non-inferiority margin of 1.5 mmHg. Assuming a treatment difference of 0 mmHg between the DE-117 arm and the Timolol arm, a standard deviation (SD) of 4.0 mmHg, and a correlation coefficient of 0.6 among repeated measures, approximately 400 adult subjects in total (200 subjects per treatment arm) will provide 90% power to demonstrate noninferiority of DE-117 Ophthalmic Solution 0.002% to Timolol Maleate Ophthalmic Solution 0.5% in IOP-lowering effect. Up to 30 pediatric subjects will be enrolled with the agreement from FDA.

The standard deviation of 4.0 mmHg was determined from previous DE-117 studies conducted in the United States: 33-002 and 33-003.

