### 8.1. Efficacy Analyses for Double-Masked Period

#### 8.1.1. Analyses of Primary Endpoint and Key Secondary Endpoints

##### 8.1.1.1. Primary Analyses

###### 8.1.1.1.1. Primary Endpoint

The primary efficacy endpoint is IOP in the study eye at each scheduled timepoint (08:00, 10:00, and 16:00) at each of three follow-up visits, Week 1, Week 6, and Month 3. The nine combinations of three scheduled timepoints at each of three follow-up visits are referred to subsequently as nine timepoints. For the primary endpoint, the following null (versus alternative) hypothesis will be tested:

$$H_0: \mu_T - \mu_C > \Delta \text{ for at least one timepoint}$$

versus

$$H_A: \mu_T - \mu_C \leq \Delta \text{ at all nine timepoints}$$

where  $\mu_T$  and  $\mu_C$  denote the mean values of the primary endpoint in the DE-117 arm and the Timolol arm, respectively, and  $\Delta$  denotes the noninferiority margin of 1.5 mmHg or 1.0 mmHg as specified below.

The primary analysis of the primary efficacy endpoint will be performed using a MMRM of IOP based on the FAS. A separate MMRM will be used for IOP at each scheduled timepoint (8:00, 10:00, or 16:00). For each scheduled timepoint, the model will include treatment ( $T_i$ ), analysis visit ( $V_j$ ), and treatment-by-visit interaction ( $TV_{ij}$ ) as fixed effects, and baseline IOP at the scheduled timepoint as a covariate. Correlations of IOP measurements within-subject will be modeled using an unstructured covariance matrix. The mathematical model is given by:

$$IOP_{ijn} = \mu + T_i + V_j + TV_{ij} + \varepsilon_{ijn}$$

where  $\mu$  denotes the overall mean, and  $\varepsilon$  denotes the random error associated with the individual subject. The above model allows treatment effect and its variability to vary over study visits.

If there are convergence issues, covariance matrix structures other than unstructured will be tried in the following order: (1) heterogeneous Toeplitz (TOEPH), (2) heterogeneous autoregressive of order 1 (ARH(1)), (3) heterogeneous compound symmetry (CSH), and (4) compound symmetry (CS). The first covariance structure that converges will be used as the primary analysis. Least squares mean IOP values for each treatment arm and differences between least squares treatment arm means and associated 95% confidence intervals will be reported for each of the nine timepoints.

The primary analysis will be repeated on pediatric subjects.

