##### 8.1.1.1.2.2. IOP at Nine Timepoints in Study Eyes with Baseline Mean Diurnal IOP $< 25$ mmHg

The second key secondary endpoint is IOP at each scheduled timepoint (08:00, 10:00, and 16:00) at each of three follow-up visits, Week 1, Week 6, and Month 3, in the study eyes with mean diurnal IOP  $< 25$  mmHg at the Baseline Visit. If noninferiority of DE-117 to Timolol for the primary endpoint and the first key secondary endpoint is achieved, the following null (versus alternative) hypothesis will be tested for the second key secondary endpoint:

$$H_{0S2}: \mu_{T2} - \mu_{C2} > \Delta, \text{ for at least one timepoint}$$

versus

$$H_{AS2}: \mu_{T2} - \mu_{C2} \leq \Delta \text{ at all nine timepoints}$$

where  $\mu_{T2}$  and  $\mu_{C2}$  denote the mean IOP values in the DE-117 arm and the Timolol arm, respectively, and  $\Delta$  denotes the noninferiority margin of 1.5 mmHg or 1.0 mmHg as specified below.

The same MMRM used in the analysis of the primary efficacy endpoint will be used for the analysis of the second key secondary endpoint. Noninferiority of DE-117 to Timolol for this endpoint (i.e., for subjects with baseline mean diurnal IOP  $< 25$  mmHg) is achieved if the upper limit of the two-sided 95% confidence interval for the difference in the mean IOP (DE-117 minus Timolol) is  $\leq 1.5$  mmHg at all nine timepoints and  $\leq 1.0$  mmHg at a majority (five or more) of the nine timepoints. Superiority of DE-117 to Timolol for this endpoint (i.e., for subjects with baseline mean diurnal IOP  $< 25$  mmHg) is achieved if the upper limit of the two-sided 95% confidence interval for the difference in the mean IOP (DE-117 minus Timolol) is  $< 0$  mmHg at all nine timepoints.

#### 8.1.1.1.2.3. Mean Diurnal IOP at Week 1

The third key secondary endpoint is mean diurnal IOP in the study eye at Week 1. If noninferiority of DE-117 to Timolol for the primary and the first two key secondary endpoints is achieved, then the following null (versus alternative) hypothesis will be tested for the third key secondary endpoint:

$$H_{0S3}: \mu_{T3} = \mu_{C3} \text{ versus } H_{AS3}: \mu_{T3} \neq \mu_{C3}$$

where  $\mu_{T3}$  and  $\mu_{C3}$  denote the mean diurnal IOP at Week 1 in the DE-117 and Timolol arm, respectively. The primary analysis of this key secondary endpoint will be performed using a MMRM analogous to the model used for the first key secondary efficacy endpoint (mean diurnal IOP at Month 3).

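### Each clock-time model for the primary endpoint adjusts only for its own baseline reading; adding the other Visit 2 readings costs almost nothing and could shrink the standard error by anything from about 0% to 11%.

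*SAP*

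**What the plan says.** SAP 8.1.1.1.1 states: "A separate MMRM will be used for IOP at each scheduled timepoint (8:00, 10:00, or 16:00"). Each model has treatment, visit, their interaction and "baseline IOP at the scheduled timepoint as a covariate". No other baseline term enters.

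SAP 8.1.1.1.2.2 carries the model over: "The same MMRM used in the analysis of the primary efficacy endpoint will be used for the analysis of the second key secondary endpoint". Step c of the pattern-mixture analysis in SAP 8.1.1.2 also reuses it.

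The unused readings exist for every adult. Inclusion criterion 9 in Protocol 8.1 begins "At all time points of IOP measurements (08:00, 10:00 and 16:00) at Visit 2 (Baseline, Day 1), have IOP of" and sets a floor of 22 mmHg in one and the same eye and a ceiling of 34 mmHg in both. For mean diurnal IOP, SAP 8.1.1.1.2.1 adjusts for the baseline diurnal mean, so that model does draw on all three readings.

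The planning inputs in SAP 3.3 include "a standard deviation (SD) of 4.0 mmHg, and a correlation coefficient of 0.6 among repeated measures". That text mentions no baseline adjustment.

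**The concern.** One tonometry reading is a noisy measure of a subject's pressure level, and two further readings from the same day carry additional information about it. Non-inferiority requires 95% upper limits of at most 1.5 mmHg at all nine timepoints and at most 1.0 mmHg at five or more, so interval width at every timepoint drives the result. The most demanding test in the hierarchy uses less baseline information than the mean diurnal endpoint ranked below it, and the SAP gives no reason. At stake is power, not validity.

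**Working it through.** **Inputs from the documents (all SAP 3.3).** Error rate and margin: "two-sided Type I error rate of 5% and a non-inferiority margin of 1.5 mmHg". The other inputs are a true difference of zero, SD 4.0 mmHg, correlation 0.6, 200 per arm and stated power 90%. The calculations assume no dropout.

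**Assumptions needed.** Let s be the correlation of a post-baseline reading with the same-clock baseline, c its correlation with a baseline at another clock time, and w the correlation among the three baseline readings. The documents give none of these separately.

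1. **The plan's 90%.** For one timepoint at margin 1.5, n per arm = 2 × 4.0² × (1.960 + 1.282)² / 1.5² = 149.4, so 150. With 200 per arm the SE is 4.0 × √(2/200) = 0.400 and power is 96.3%. Unadjusted with correlation 0.6, simulation gives 83.8% for all nine limits at or below 1.5, and 72% for the full rule. None of these is 90%. Choices that the plan does not state do come close: three timepoints at 1.5 (91.5%), or the full rule with own-clock adjustment and 10-15% loss (91.9% to 89.3%). The 90% therefore cannot be traced, but it is not shown to be wrong.

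2. **One reading against three, 0.6 for every pair.**
   - Own reading: R² = 0.6² = 0.36; residual SD = 4.0 × √0.640 = 3.20; SE = 3.20 × √(2/200) = 0.320.
   - All three: R² = 3s²/(1 + 2w) = 1.08/2.2 = 0.491; residual SD = 4.0 × √0.509 = 2.85; SE = 0.285.
   - Ratio: √(0.509/0.640) = 0.892, a 10.8% reduction. Simulated ANCOVA with 200 per arm gives 10.7-10.8%.

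3. **Other correlations.** With s, c, c as the three baseline correlations, R² = [s² + 2c² − w(s + 2c)²/(1 + 2w)]/(1 − w). For s = 0.6, c = 0.5, w = 0.8: (0.86 − 0.8 × 2.56/2.6)/0.2 = 0.3615, and 1 − √(0.6385/0.640) = 0.1%.

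| s | c | w | SE reduction |
|---|---|---|---|
| 0.6 | 0.6 | 0.6 | 10.8% |
| 0.5 | 0.5 | 0.5 | 8.7% |
| 0.4 | 0.4 | 0.4 | 6.6% |
| 0.3 | 0.3 | 0.3 | 4.4% |
| 0.6 | 0.6 | 0.7 | 7.3% |
| 0.6 | 0.6 | 0.8 | 4.4% |
| 0.6 | 0.6 | 0.9 | 2.0% |
| 0.6 | 0.5 | 0.6 | 3.5% |
| 0.6 | 0.5 | 0.7 | 1.4% |
| 0.6 | 0.5 | 0.8 | 0.1% |

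4. **Eligibility truncation.** Simulated with SD 4.0 before selection and all three baselines restricted to 22-34 mmHg. With 0.6 for every pair and an assumed pre-selection mean of 24, SE is 0.305 against 0.285 (6.5% smaller); means of 22 and 26 give 5.8% and 7.0%. At mean 24, w = 0.8 gives about 3%, and adding c = 0.5 gives about 0.1%.

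5. **Power for the full nine-timepoint rule, 0.6 for every pair.** After own-reading adjustment the residual correlation is (0.6 − 0.36)/0.64 = 0.375 within a clock time and (0.6 − 0.72 + 0.216)/0.64 = 0.15 across clock times.

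| True difference (mmHg) | Own reading | All three |
|---|---|---|
| 0 (plan) | 95.6% | 99.2% |
| 0.25 | 67% | 84% |
| 0.5 | 19% | 32% |

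In the truncated case at mean 24, the figures are 75% and 84% at 0.25 mmHg, and 25% and 32% at 0.5 mmHg.

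6. **Subgroup with baseline mean diurnal IOP below 25 mmHg.** In the truncated setting of step 4, R² is about 0.005 with one reading and 0.030 with three, so the reduction is 1 − √(0.970/0.995) = 1.3% (1.2-1.3% over the three assumed means).

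7. **Replacing instead of adding.** If the diurnal mean replaces the own reading, R² = (s + 2c)²/[3(1 + 2w)]. For s = 0.6, c = 0.5, w = 0.8 this is 2.56/7.8 = 0.328, and √(0.672/0.640) = 1.025: the SE rises by 2.5%.

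**The case against.** The planned model is conventional covariate adjustment. It has no bias and no Type I error problem, and it contradicts nothing else in the SAP. The other readings are not thrown away either: they help select the study eye and form the diurnal baseline. All of that stands, so this is a recommendation on efficiency and not the correction of an error.

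A reader might infer a gain of 6-11% as a property of the trial. The documents do not support that. SAP 3.3 gives one correlation and does not say whether it reaches back to baseline or applies across clock times; within-day correlation above 0.6, or weaker cross-clock prediction, cuts the gain as step 3 shows. The truncated case also applies SD 4.0 before selection, which brings the post-baseline SD down to about 3.3, whereas the SAP uses 4.0 for the trial population. The percentage reduction is safer to quote from that case than the SE or the power.

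A reader might also expect the smaller subgroup to benefit most. It does not: readings of at least 22 with a mean below 25 leave little baseline spread, and the gain is about 1%.

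Finally, under 0.6 for every pair, the existing covariate already gives about 96% power at the plan's assumed difference. The practical benefit is larger only if the true difference is above 0, or if 4.0 is already a baseline-adjusted SD. In that last case full-rule power is 72%, and an SE 6-11% smaller would bring it to about 79-84%.

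**Conclusion.** The point holds as a low-cost gain in precision of uncertain size. The SE reduction is about 11% if 0.6 applies to every pair of readings, and about 6-7% after eligibility truncation with an assumed pre-selection mean near 24 mmHg. It is about 0-5% once within-day correlation reaches 0.8 or cross-clock correlation falls to 0.5. With the same-time reading kept in the model, the large-sample SE cannot rise, so the recommendation does not depend on which figure is right. Nothing here makes the planned analysis invalid or shows the stated 90% power to be wrong.

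**What to change.** Before unmasking, amend SAP 8.1.1.1.1 so that each of the three models keeps the same-time baseline and also includes baseline mean diurnal IOP (1 degree of freedom) or the other two Visit 2 readings (2 degrees of freedom). State which. Make the same change in the model step of the pattern-mixture analysis (SAP 8.1.1.2, step c). Do not replace the same-time baseline.

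Handle a missing baseline reading by the existing rule in SAP 4.2.2. This matters mainly for the up to 30 children, whose readings depend on cooperation; no second rule is needed. The model may be carried to SAP 8.1.1.1.2.2 for consistency, with little gain expected there.

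The sponsor could look up the within-day and cross-clock correlations in studies 33-002 and 33-003, which SAP 3.3 names as the source of the SD. The change should not wait for that. Protocol 14.7.1 leaves model details to the SAP, so the cost is one sentence, one line of code, and 1-2 degrees of freedom out of about 400, with no new data for adults.

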#### 8.1.1.1.2. Key Secondary Endpoints

##### 8.1.1.1.2.1. Mean Diurnal IOP at Month 3

The first key secondary endpoint is the mean diurnal IOP in the study eye at Month 3. The following null (versus alternative) hypothesis will be tested:

$$H_{0SI}: \mu_{TI} - \mu_{CI} > \Delta \text{ versus } H_{ASI}: \mu_{TI} - \mu_{CI} \leq \Delta$$

where  $\mu_{TI}$  and  $\mu_{CI}$  denote the mean diurnal IOP at Month 3 in the DE-117 and Timolol arm, respectively, and  $\Delta$  denotes the noninferiority margin of 1.5 mmHg. The primary analysis of this key secondary efficacy endpoint will be performed using a MMRM based on the FAS. The model will include treatment, analysis visit (Week 1, Week 6, or Month 3), and treatment-by-visit interaction as fixed effects, and baseline mean diurnal IOP as a covariate. Correlations of mean diurnal IOPs within-subject will be modeled using an unstructured covariance matrix. The mathematical model is analogous to the model in the primary efficacy endpoint.

If there are convergence issues, covariance matrix structures other than unstructured will be tried in the following order: (1) heterogeneous Toeplitz (TOEPh), (2) heterogeneous autoregressive of order 1 (ARH(1)), (3) heterogeneous compound symmetry (CSH), and (4) compound symmetry (CS). The first covariance structure that converges will be used as the primary analysis. Least squares mean diurnal IOP values at Month 3 for each treatment arm and the difference between least squares treatment group means and its 95% confidence interval will be reported.

Noninferiority of DE-117 to Timolol is achieved for this endpoint if the upper limit of the 95% confidence interval for the difference between DE-117 and Timolol (DE-117 minus Timolol) in the mean diurnal IOP at Month 3 is  $\leq 1.5$  mmHg. Superiority of DE-117 to Timolol is achieved for this endpoint if the upper limit of the 95% confidence interval is  $< 0$  mmHg.

This key secondary endpoint analysis will be repeated on pediatric subjects.

##### 8.1.1.1.2.2. IOP at Nine Timepoints in Study Eyes with Baseline Mean Diurnal IOP $< 25$ mmHg

The second key secondary endpoint is IOP at each scheduled timepoint (08:00, 10:00, and 16:00) at each of three follow-up visits, Week 1, Week 6, and Month 3, in the study eyes with mean diurnal IOP  $< 25$  mmHg at the Baseline Visit. If noninferiority of DE-117 to Timolol for the primary endpoint and the first key secondary endpoint is achieved, the following null (versus alternative) hypothesis will be tested for the second key secondary endpoint:

$$H_{0S2}: \mu_{T2} - \mu_{C2} > \Delta, \text{ for at least one timepoint}$$

versus

$$H_{AS2}: \mu_{T2} - \mu_{C2} \leq \Delta \text{ at all nine timepoints}$$

where  $\mu_{T2}$  and  $\mu_{C2}$  denote the mean IOP values in the DE-117 arm and the Timolol arm, respectively, and  $\Delta$  denotes the noninferiority margin of 1.5 mmHg or 1.0 mmHg as specified below.

The same MMRM used in the analysis of the primary efficacy endpoint will be used for the analysis of the second key secondary endpoint. Noninferiority of DE-117 to Timolol for this endpoint (i.e., for subjects with baseline mean diurnal IOP  $< 25$  mmHg) is achieved if the upper limit of the two-sided 95% confidence interval for the difference in the mean IOP (DE-117 minus Timolol) is  $\leq 1.5$  mmHg at all nine timepoints and  $\leq 1.0$  mmHg at a majority (five or more) of the nine timepoints. Superiority of DE-117 to Timolol for this endpoint (i.e., for subjects with baseline mean diurnal IOP  $< 25$  mmHg) is achieved if the upper limit of the two-sided 95% confidence interval for the difference in the mean IOP (DE-117 minus Timolol) is  $< 0$  mmHg at all nine timepoints.

#### 8.1.1.1.2.3. Mean Diurnal IOP at Week 1

The third key secondary endpoint is mean diurnal IOP in the study eye at Week 1. If noninferiority of DE-117 to Timolol for the primary and the first two key secondary endpoints is achieved, then the following null (versus alternative) hypothesis will be tested for the third key secondary endpoint:

$$H_{0S3}: \mu_{T3} = \mu_{C3} \text{ versus } H_{AS3}: \mu_{T3} \neq \mu_{C3}$$

where  $\mu_{T3}$  and  $\mu_{C3}$  denote the mean diurnal IOP at Week 1 in the DE-117 and Timolol arm, respectively. The primary analysis of this key secondary endpoint will be performed using a MMRM analogous to the model used for the first key secondary efficacy endpoint (mean diurnal IOP at Month 3).

For the primary and key secondary efficacy endpoints, the testing sequence and multiplicity adjustment details are provided in [Section 6.4](#).

This key secondary endpoint analysis will be repeated on pediatric subjects.

#### 8.1.1.2. Sensitivity Analyses

For the primary endpoint and the key secondary endpoints, sensitivity analyses will be performed to assess the robustness of the results from the primary analysis. The sensitivity analyses consist of two types: (1) assessment based on the PPS and (2) a pattern-mixture model (PMM) approach ([Table 8](#)). Unless otherwise specified, for subjects who receive IOP-lowering rescue therapy, any IOP values collected after the receipt of rescue therapy will be censored (i.e., treated as missing) in the analyses.

**Table 8: Overview of Primary and Sensitivity Analysis Methods**

| Primary or Sensitivity Analysis | Statistical Method        | Analysis Population | Handling of Missing Data |
|---------------------------------|---------------------------|---------------------|--------------------------|
| Primary Analysis                | MMRM                      | FAS                 | Observed cases           |
| Sensitivity Analyses            | MMRM                      | PPS                 | Observed cases           |
|                                 | PMM with delta-adjustment | FAS                 | MI                       |

Abbreviations: FAS = full analysis set; MI = multiple imputation; MMRM = mixed-effects model for repeated measures; PMM = pattern-mixture model; PPS = per protocol set.

To assess the sensitivity to departure from MAR assumption, a PMM with delta-adjustment will be applied, as follows:

- a. Use Markov chain Monte Carlo (MCMC) to create monotone missingness first. Then obtain standard multiple imputations under MAR assumptions for missing IOP values using monotone regression. The missing data are filled in and 50 complete datasets are created. The seed that will be used in the SAS program is 13546.
- b. For each IOP value that had been missing because of (1) censoring after having received IOP-lowering rescue therapy; or because of (2) early study discontinuation due to lack of efficacy or AE, regardless of treatment arm, adjust these values by adding delta to the imputed values, where delta = 1.0 mmHg. The seed that will be used in the SAS program is 13546.
- c. Each of the 50 complete datasets will then be analyzed separately using the same MMRM as used for the primary analysis.
- d. The estimates obtained from the MMRM analysis of each complete dataset are combined for inference purposes.
- e. Repeat step b, c, d, with delta = 2.0, 3.0, 4.0, and 5.0 mmHg. The larger the value of delta that is required to reverse the conclusion of the primary analysis, the more robust the conclusion is considered to be.

The main part of the SAS code for the specified MMRM analysis and PMM are provided in [Appendix A](#) and [Appendix B](#), respectively.

For the primary endpoint, in addition to the two types of sensitivity analyses described above, if the overall rate of study drug discontinuation due to lack of efficacy or AE is greater than 10% and the difference between the rate in the DE-117 and Timolol arms is greater than 5 percentage points, a trimmed mean analysis ([Permutt et al., 2017](#)) will be conducted as a sensitivity analysis.

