### **3.4. Visits and Assessments**

There are 5 scheduled visits for pediatric subjects and 9 scheduled visits for adult subjects. Assessments at each visit and the time/visit window for each post-baseline assessment are specified in the Assessment Schedule for adult ([Table 1](#)) and pediatric subjects ([Table 2](#)), respectively.

If the study drug administration is discontinued prior to Visit 5 (end of the double-masked treatment period), the subject should be encouraged to still participate in follow-up study visits until Visit 5 on an observational basis. For subjects whose study participation is terminated prior to Visit 8 (Month 12), to the extent possible, all assessments scheduled for Visit 8 (Month 12) will be performed at the Exit Visit.

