## 6.2. Handling of Missing Data

### 6.2.1. Efficacy Measures

For subjects with the use of any non-study IOP-lowering therapy to lower IOP, unless otherwise specified, the IOP data collected after the non-study IOP-lowering therapy will be censored (treated as missing) in efficacy analyses in both double-masked and open-label periods.

For efficacy measures during double-masked period,

- For each IOP endpoint, no imputation is needed for the analysis on observed cases using the mixed-effects model for repeated measures (MMRM). Sensitivity analysis will be performed using a Pattern-Mixture Model (PMM) approach.
- In the PMM approach, Multiple Imputation (MI) with mixed missing data mechanisms will be used to investigate the appropriateness of the missing at random (MAR) assumption for missing values resulting from censoring due to the use of IOP-lowering rescue therapy, or resulting from study discontinuation due to lack of efficacy or AE.

For efficacy measures during open-label treatment period, no inferential analysis will be performed. Summary statistics will be provided for IOP and mean diurnal IOP for each scheduled visit, using observed data.

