## 7. SUMMARY OF STUDY POPULATION DATA

### 7.1. Subject Disposition

The disposition of ITT population (i.e., all randomized subjects) will be summarized by treatment period (double-masked and open-label) and by planned treatment (for double-masked period) and overall.

For the double-masked period, the summary will include the number and percentage of ITT subjects in the Safety population, FAS, and PPS. The disposition summary will also include the number and percentage of subjects who completed the study drug, subjects who discontinued the study drug prematurely but continued with study participation until the Month 3 Visit and among which who completed or not completed the Month 3 Visit, as well as the number and percentage of subjects who discontinued from the study or discontinued from the study drug prior to Month 3 Visit by the primary discontinuation reason.

For the open-label period, the summary will include the number and percentage of subjects who received any study treatment during open-label period, and subjects who are still on the study at the time of data cut (for reports other than the final clinical study report). The disposition summary will also include the number and percentage of subjects who completed the study drug, and subjects who discontinued from the study prior to Month 12 Visit by the primary discontinuation reason.

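### The delta-adjusted sensitivity analysis leaves some subjects who stop study drug for lack of efficacy or AE unshifted, so its tipping delta can be misstated in either direction

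*SAP*

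**What the plan says.** SAP 8.1.1.2 imputes missing IOP under MAR, then in step b adds delta to two groups of imputed values. The first is missing because of "censoring after having received IOP-lowering rescue therapy". The second is missing because of "early study discontinuation due to lack of efficacy or AE, regardless of treatment arm". SAP 6.2.1 uses the same pair of categories, the second worded "or resulting from study discontinuation due to lack of efficacy or AE", so the choice of study discontinuation is not a slip in one place. Delta starts at 1.0 mmHg, and step e extends the grid: "Repeat step b, c, d, with delta = 2.0, 3.0, 4.0, and 5.0 mmHg". Step e also says how to read the result: the larger the delta needed to reverse the conclusion, the more robust it is.

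Elsewhere the plan treats stopping drug and leaving the study as separate events. SAP 3.4 says that if drug is stopped before Visit 5, "the subject should be encouraged to still participate in follow-up study visits until Visit 5 on an observational basis". Protocol 8.5 says the same, and its list of reasons for stopping drug or ending participation includes voluntary withdrawal and loss to follow-up. SAP 7.1 counts "subjects who discontinued the study drug prematurely but continued with study participation until the Month 3 Visit", split by whether they completed Month 3, and tabulates the reason for stopping drug as well as for leaving the study.

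The trimmed-mean analysis at the end of SAP 8.1.1.2 looks at drug discontinuation instead. It is run "if the overall rate of study drug discontinuation due to lack of efficacy or AE is greater than 10" per cent and the arms differ by more than 5 percentage points.

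**The concern.** The plan creates a group that is off drug but on study, expects some of them to miss Month 3, and has no rule that carries the reason for stopping drug forward to later missing values. Some treatment failures therefore get no delta. MAR is hard to defend for them. If a subject's last readings were taken on the day drug was stopped, the imputation rests on IOP that may still reflect drug effect.

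This matters because the pattern-mixture analysis is the only sensitivity analysis that always departs from MAR. SAP 10.3 drops last-observation-carried-forward on the ground that the pattern-mixture analysis is sufficient, the per-protocol analysis uses observed cases, and the trimmed mean is conditional and covers only the primary endpoint. A measure of robustness should not turn on which exit reason a site records after a drug failure.

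**Working it through.** **1. The plan's own figure.** SAP 3.3 gives "a two-sided Type I error rate of 5% and a non-inferiority margin of 1.5 mmHg", a true difference of 0, SD 4.0, correlation 0.6, 200 adults per arm and 90% power.

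- SE = 4.0 × √(2/200) = 0.40 mmHg.
- One timepoint against 1.5: Φ(1.5/0.40 − 1.96) = Φ(1.79) = 96.3%.
- Three visits at one clock time, all against 1.5, correlation 0.6: 91.6% by simulation (400,000 draws), close to the stated 90%. The SAP does not say which calculation was used.

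The stated power does not depend on the gap discussed here.

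**2. Who falls through.** Take a subject who stops drug for lack of efficacy or AE before Visit 5.

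| What happens next | Handling |
|---|---|
| Receives other IOP-lowering therapy | Later IOP censored, imputed, delta added (first trigger) |
| No rescue; leaves the study with lack of efficacy or AE recorded | Imputed, delta added (second trigger) |
| No rescue; attends visits | Observed IOP is used |
| No rescue; stays, then misses visits | Imputed under MAR, no delta |
| No rescue; stays, then leaves as voluntary withdrawal or lost to follow-up | Imputed under MAR, no delta |

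The last two rows are the gap.

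**3. Size.** Let uT and uC be the shares of the DE-117 and timolol arms in those two rows at a given timepoint. Step b shifts both arms alike, so the shift left out of the treatment difference (DE-117 minus timolol) is delta × (uT − uC). The documents give no discontinuation rates, so every u below is an assumption.

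This was checked by simulated multiple imputation with ANCOVA at Month 3: 200 per arm, 10 imputations, 400 replicates, true difference 0, SD 4.0, correlation 0.6, and already-penalized shares assumed at 4% DE-117 and 2% timolol. Results at delta 5:

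| uT v uC | Omitted shift, mmHg | Mean upper 95% limit, current rule → extended rule |
|---|---|---|
| 1% v 1% | 0 | 0.763 → 0.770 |
| 2% v 1% | 5 × 0.01 = +0.05 | 0.742 → 0.802 |
| 3% v 1% | 5 × 0.02 = +0.10 | 0.767 → 0.880 |
| 5% v 1% | 5 × 0.04 = +0.20 | 0.786 → 1.006 |
| 1% v 3% | 5 × (−0.02) = −0.10 | 0.783 → 0.696 |

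At delta 1 the same cases give −0.02 to +0.04 mmHg. With a true difference of 0, none of these mean limits reaches 1.5; only the 5% v 1% case crosses 1.0, and only just.

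**4. Effect on the tipping delta.** Hold the SE fixed. Let UL be the upper limit before any delta, p the arm difference already penalized, and e = uT − uC. The upper limit reaches 1.5 at (1.5 − UL)/p under the current rule and at (1.5 − UL)/(p + e) under the extended one.

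| UL | p | e | Current rule | Extended rule |
|---|---|---|---|---|
| 1.4 | 0.02 | +0.01 | 0.1/0.02 = 5.0 | 0.1/0.03 = 3.3 |
| 1.4 | 0.04 | +0.02 | 0.1/0.04 = 2.5 | 0.1/0.06 = 1.7 |
| 1.2 | 0.04 | +0.02 | 0.3/0.04 = 7.5 | 0.3/0.06 = 5.0 |
| 1.2 | 0.02 | +0.01 | 0.3/0.02 = 15 | 0.3/0.03 = 10 |
| 1.4 | 0.02 | −0.01 | 0.1/0.02 = 5.0 | 0.1/0.01 = 10 |

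The first three rows show a change that the 1-to-5 grid could register or just reach. In the fourth, both values lie beyond the grid and the report would read the same. The fifth shows the opposite direction.

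**5. Whether the trimmed mean covers the gap.** It needs both thresholds. Drug discontinuation of 12% v 8% (overall 10%, difference 4 points) does not trigger it, nor does 10% v 4% (overall 7%, difference 6 points).

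**The case against.** The strongest reply is that the gap is narrow. The subject must stop drug for one of two reasons, take no rescue, stay on study, then go missing, and any study exit must carry a different reason. Several features narrow it further:

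- Protocol 8.5 asks for early-termination procedures on the day drug is stopped, to the extent possible. Under the schedule these include IOP at all three clock times.
- The wide windows in SAP Table 4 (days 2–22, 23–61, and 62 to the Month 3 visit) often turn that visit into an observed value for its window.
- Off-drug IOP without rescue is kept and informs the imputation.
- The protocol's example of lack of efficacy is IOP above 34 mmHg. How often such subjects go without other therapy is unknown; those who receive it are caught by the rescue trigger.

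All of this stands, and it limits how many subjects are affected. It does not close the gap: a stop-day visit fills one window and leaves later ones missing.

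Three stronger readings are tempting and should not be drawn. A reader might infer that delta applies only to study discontinuation; the rescue trigger contradicts that. A reader might infer that robustness is overstated; delta is added in both arms, so that follows only if DE-117 has more of the uncaptured subjects, and nothing in the documents says so. A reader might take the trimmed-mean condition as a rival definition of treatment failure; it is a threshold for running another analysis, and does not say which imputed values are shifted. The contrast shows only that the drug-stop reason was available and was used a paragraph later.

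The Appendix B program is not in the available text, so how it flags these values cannot be checked.

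**Conclusion.** The point holds in limited form. As written, step b and 6.2.1 leave some drug failures without delta in the plan's only unconditional departure from MAR. The resulting error in the tipping delta has no known sign: about zero if the arms are alike, overstating robustness with a DE-117 excess, conservative with a timolol excess. The sizes in the working rest on assumed shares of 1% to 5% per arm and, for the tipping values, a fixed SE. They describe Month 3 and should not be applied unchanged to all nine timepoints, since missingness accumulates over visits.

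A result well inside the bounds would not be disturbed. A result near 1.5 mmHg, or one relying on the 1.0 mmHg bound at just five timepoints, could have its robustness misread. The primary analysis, the Type I error rate and the non-inferiority rule are untouched. This is a change the sponsor should make because it is cheap; no fault in the main inference has been shown.

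**What to change.** In step b of SAP 8.1.1.2 and in 6.2.1, add delta to every imputed value that is missing after rescue, or after discontinuation of study drug or of the study for lack of efficacy or AE, whatever reason is later recorded for missed visits or for leaving. Report, by arm and timepoint, how many values are shifted under each trigger, so the reader can see p and e directly. Check that the Appendix B program sets its flag the same way.

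The cost is one sentence in two places and one extra flag in the program. The drug-stop reason is already needed for the disposition table in SAP 7.1, so no new data are required. The sponsor accepts that the reported tipping delta may come out smaller. The wording should be settled before unmasking.
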